7.1.3 Serious Adverse Events

If an AE (not limited to AEs of Special Interest) meets any of the following criteria, it is to be reported to AbbVie as a SAE within 24 hours of the site being made aware of the event.

Death of Patient	An event that results in the death of a patient.
Life-Threatening	An event that, in the opinion of the investigator, would have resulted in immediate fatality if medical intervention had not been taken. This does not include an event that would have been fatal if it had occurred in a more severe form.
Hospitalization	An event that results in an admission to the hospital for any length of time. This does not include an emergency room visit or admission to an outpatient facility.
Prolongation of Hospitalization	An event that occurs while the patient is hospitalized and prolongs the patient's hospital stay.
Congenital Anomaly	An anomaly detected at or after birth, or any anomaly that results in fetal loss.

Obvie HUMIRA® (adalimumab) P10-023 Protocol Amendment 3 Psoriasis HUMIRA® Registry

Persistent or **Significant** Disability/Incapacity An event that results in a condition that substantially interferes with the activities of daily living of a patient. Disability is not intended to include experiences of relatively minor medical significance such as headache, nausea, vomiting, diarrhea, influenza, and accidental trauma (e.g., sprained ankle).

Important Medical Event Requiring Medical or Surgical Intervention to Prevent Serious Outcome

An important medical event that may not be immediately life-threatening or result in death or hospitalization, but based on medical judgment may jeopardize the patient and may require medical or surgical intervention to prevent any of the outcomes listed above (i.e., death of patient, life-threatening, hospitalization, prolongation of hospitalization, congenital anomaly, or persistent or significant disability/incapacity). Examples of such events include allergic bronchospasm requiring intensive treatment in an emergency room or at home, blood dyscrasias or convulsions that do not result in inpatient hospitalization, or the development of drug dependency or drug abuse.

Spontaneous Abortion

Miscarriage experienced by patient.

Elective Abortion

Elective abortion performed on patient.

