10.0 Data Analysis Plan

10.1 Analyzable Populations

All Treated Patient Population is defined as patients who receive at least one dose of HUMIRA® in the registry.

New Prescription Patient Population is defined as patients who have newly initiated HUMIRA[®] therapy within 4 weeks prior to the entry into the registry and who receive at least one dose of HUMIRA[®] in the registry (the New Prescription Population is a subset of the All Treated Patient Population).

The All Treated Patient Population and the New Prescription Patient Population will be used for safety and effectiveness analysis.

In addition, the Intermittent Treatment Population, defined as patients who have at least 2 treatment interruption periods with at least 3 treatment periods (Figure 1), will be used for the safety analysis. A treatment interruption period is defined as greater than 70 consecutive days during which the patient does not receive any HUMIRA® treatment. The treatment interruption period starts from 71 days after the last dose of HUMIRA® in

the preceding treatment period and up to the day prior to the first dose of $HUMIRA^{@}$ in the subsequent period. A treatment period is defined as at least one dose of $HUMIRA^{@}$ up to 70 days after the last dose of $HUMIRA^{@}$.

Last Dose First Dose First Dose Day 70 Post-TI (#1) Pre-TI (#1) On Drug Off Drug = TI Drug On 70 days after last dose Treatment Period 1 -Treatment Interruption 1 -**Treatment Period** through 70 days after last dose Begins Day 71 after last dose 2, 3....N

[figure not shown]
Figure 1. Treatment Period and Treatment Interruption (TI) Period

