10.3 Safety Analyses

[figure not shown]
Five main safety analyses will be reported from this registry: four analyses will summarize data through the end-of-registry (as defined in Section 12.0) and one will exclude the HCP Process. The details of the analyses are in Section 10.3.1, Section 10.3.2, and Section 10.3.3. If a patient is not covered by any of the analysis populations, but experiences an AE, this AE will be reported in a separate listing.

Observational AEs: SAEs, AEs of Special Interest and AEs that lead to permanent discontinuation of HUMIRA[®] occurring from the first day in the registry (enrollment visit or date of informed consent, through the last contact (as defined in Section 10.3.1) irrespective of drug treatment duration.

Registry Treatment-emergent AEs: SAEs, AEs of Special Interest and AEs that lead to permanent discontinuation of HUMIRA® occurring from the first recorded dose of HUMIRA® in the registry through 70 days after the last dose excluding AEs occurring during treatment interruptions (as defined in Section 10.1).

All Treatment Emergent AEs: SAEs, AEs of Special Interest and AEs that lead to permanent discontinuation of HUMIRA® occurring from the first recorded dose of HUMIRA® (initial dose) through 70 days after the last dose excluding AEs occurring during treatment interruptions (as defined in Section 10.1.

AEs for intermittent treatment: SAEs, AEs of Special Interest and AEs that lead to permanent discontinuation of HUMIRA® in the Intermittent Treatment Population.

Observational AEs excluding HCP process: SAEs, AEs of Special Interest and AEs that lead to permanent discontinuation of HUMIRA® occurring from the first day in the registry through the last contact excluding the HCP process.

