10.3.3 Analysis of AEs for Intermittent Treatment

The following analyses will be performed for the Intermittent Treatment:

- 1. Rates (event per 100 patient-years of exposure to HUMIRA®) of treatment-emergent SAEs, AEs of Special Interest and AEs that lead to permanent discontinuation of HUMIRA® and the 95% confidence interval will be provided.
- 2. Rates (event per 100 patient-years) of SAEs, AEs of Special Interest and AEs that lead to permanent discontinuation of HUMIRA® and the 95% confidence interval over the course of intermittent treatment strategy, defined as from the first day of HUMIRA® injection to the end of the last treatment period, will be provided.

To further evaluate the effect of intermittent treatment on the AE profile, rates of AEs per 100 patients-years of exposure to HUMIRA® will be analyzed for each treatment period for the subgroups of patients with at least 3, 4, and 5 or more TIs.

	Overall	1 st Treatment Period	2 nd Treatment Period	3 rd Treatment Period	4 th Treatment Period	5 th Treatment Period	6 th + Treatment Period
> 2 TIs ^a	X.XX	X.XX	X.XX	x.xx			
> 3 TIs	X.XX	X.XX	X.XX	x.xx	X.XX		
> 4 TIs	X.XX	X.XX	X.XX	x.xx	x.xx	X.XX	
> 5 TIs	X.XX	X.XX	X.XX	x.xx	x.xx	X.XX	X.XX

a. This is the Intermittent Treatment Population.

Summaries of AEs among patients not in the Intermittent Treatment Population will be provided as a reference.

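### The Intermittent Treatment Population is selected by later restarts, so fatal and therapy-ending events cannot appear in its early periods and the period and reference comparisons are biased

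*Protocol*

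**What the plan says.** - **Membership.** Section 10.1 of the protocol names the "Intermittent Treatment Population, defined as patients who have at least 2 treatment interruption periods with at least 3 treatment periods".
- **Interruption.** The same section says "A treatment interruption period is defined as greater than 70 consecutive days during which the patient does not receive any HUMIRA® treatment". The interruption lasts "up to the day prior to the first dose of" drug in the next period, so only a restart completes it. A final stop is not an interruption.
- **Events counted.** Section 10.3 lists "SAEs, AEs of Special Interest and AEs that lead to permanent discontinuation of HUMIRA® in the Intermittent Treatment Population". Under Section 7.1.3 one SAE criterion is "An event that results in the death of a patient".
- **Analysis.** Section 10.3.3 gives its purpose as follows: "To further evaluate the effect of intermittent treatment on the AE profile, rates of AEs per 100 patients-years of exposure" are to be analysed for each treatment period. There are further rows for patients with at least 3, 4 and 5 interruptions. It also asks for a whole-strategy rate that starts at the first injection.
- **Reference.** Section 10.3.3 adds: "Summaries of AEs among patients not in the Intermittent Treatment Population will be provided as a reference".

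Nothing in these sections makes membership depend on time, uses a landmark, or starts the intermittent clock at the third treatment period.

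**The concern.** Membership is known only after the second restart, but events and exposure are counted from the first dose. The first two periods of every member are therefore time during which the patient could not have died or stopped for good. This is immortal-time selection. The patients who did die or stop in those periods are in the comparison group.

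The section says that it evaluates an effect of intermittent treatment, and its layout invites reading along a row and against the reference. A rise on re-treatment, or a favourable contrast with other patients, could come from selection alone. It is one of the five main safety analyses of Section 10.3, in a registry that Section 4.0 describes as a post-marketing commitment to FDA and EMA.

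**Working it through.** The protocol gives no figure for this analysis and no rates of interruption, restart or discontinuation. There is thus no planned number to reproduce, and the sample-size calculation in Section 10.6 does not bear on the point.

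**Step 1: what follows from the definitions alone.** To be in a row that needs at least *k* interruptions, a patient must restart *k* times and so must come alive and treatable through periods 1 to *k*.

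| Row (interruptions required) | Periods where fatal or truly therapy-ending events are impossible |
|---|---|
| at least 2 | 1–2 |
| at least 3 | 1–3 |
| at least 4 | 1–4 |
| at least 5 | 1–5 |

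The one exception is an AE recorded as leading to permanent discontinuation in a patient who restarts later. The whole-strategy rate includes the same event-free time in its denominator.

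**Step 2: therapy-ending events, simulated.** Assumed constant rates per 100 patient-years: 5 non-terminating AEs, 3 therapy-ending AEs, 10 other permanent stops, 30 interruptions. Mean time off drug is 0.5 year, follow-up 10 years.
- Therapy-ending rate in periods 1, 2, 3 of the intermittent row: 0.00, 0.00, 3.01.
- Overall: 1.37 in the intermittent group and 5.46 in the reference, where the true rate is 3.0 in both.
- Non-terminating AEs unrelated to interruption: 4.9, 5.0, 5.0, and 5.0 in the reference. These are unbiased.

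**Step 3: all SAEs together.** Assumed: true rate 8.0 per 100 patient-years in every period, other permanent stops 0.1 per year, a 0.5-year gap, 10 years. Let *q* be the share of SAEs that end therapy. If no SAE triggers an interruption, only the non-ending SAEs can be seen in periods 1 and 2, so the expected early rate is 8.0 × (1 − *q*):
- *q* = 0.05: 8.0 × 0.95 = 7.6
- *q* = 0.20: 8.0 × 0.80 = 6.4
- *q* = 0.40: 8.0 × 0.60 = 4.8

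The simulated rates agree within simulation error:

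| SAEs ending therapy | SAEs triggering an interruption | Other interruptions per year | Periods 1, 2, 3 | Intermittent vs reference, overall |
|---|---|---|---|---|
| 5% | 0 | 0.4 | 7.6, 7.7, 8.0 | 7.8 vs 8.6 |
| 20% | 0 | 0.4 | 6.5, 6.2, 8.0 | 7.2 vs 10.0 |
| 40% | 0 | 0.4 | 4.9, 5.0, 8.1 | 6.5 vs 12.1 |
| 10% | 20% | 0.3 | 8.3, 8.2, 8.0 | 8.1 vs 7.8 |
| 10% | 20% | 0.15 | 9.9, 9.5, 7.9 | 9.0 vs 7.4 |

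The last two rows allow some SAEs to cause a temporary interruption, which Section 6.5 permits because therapy may be interrupted for any reason. Such events help a patient to qualify, so they are over-represented in the early periods and the trend turns round.

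**Step 4: the alternative layout.** If every treated patient contributes to each period actually reached, the same model returns about 8.0 in every period.

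**The case against.** A reader might infer that every period trend and every contrast with the reference is an artefact, and that the table is bound to show rates rising on re-treatment and intermittent users as safer. The documents do not support that. Many collected events need not end therapy, such as a short hospital admission, a non-serious opportunistic infection, non-melanoma skin cancer or diverticulitis. If they do not affect interruption either, their rates are unbiased. Events that prompt a temporary interruption are biased the other way. A large apparent rise, such as 4.9 to 8.1, mainly reflects the assumed 40% share; at 5% it is only a few per cent. These objections stand and limit the point.

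It is also fair that the analysis is descriptive, has no test or decision rule, and calls the non-members a reference only. The observational and treatment-emergent analyses in Sections 10.3.1 and 10.3.2 do not select on restart, so no event is lost to the registry. This lowers the weight of the point but does not answer it. The section states that it evaluates an effect, and the protocol itself fixes the population, the clock, the table and the reference group, so the matter is not one left open for the SAP.

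The remedy is not perfect either. Patients who reach later periods are still a selected set. With assumed differences in risk between patients (frailty) and no effect of interruption, the time-dependent layout gave 7.5, 7.4, 7.0, a small false fall.

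**Conclusion.** The defect is real and narrower than a general claim of artefact. For fatal events and AEs that truly end therapy, the early-period zeros are forced by the definition and need no assumed hazard. For these events neither the trend across periods nor the reference comparison can be interpreted. For other SAEs and AEs of Special Interest there are three cases:
- no bias, if the event neither ends nor interrupts therapy;
- early rates too low, if it sometimes ends therapy;
- early rates too high, if it triggers a temporary interruption.

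The net direction and size for these other events are unknown. The figures above illustrate the range under constant hazards and assumed shares, none of which comes from the protocol. This is a should-fix: it affects one of five main safety analyses and leaves the All Treated analyses intact.

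**What to change.** In Section 10.3.3, make intermittent status time-dependent:

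1. Let every All Treated patient contribute events and exposure to each treatment period actually reached, and give rates by current period among all who reached it.
2. Count person-time as intermittent only from the start of the third treatment period, and put earlier time in the reference.
3. Use this layout to evaluate the effect of intermittent treatment. If the present table is kept, label it as conditional on later restart and state that fatal and therapy-ending events are excluded from its early periods by definition.
4. State that later periods still contain a selected set of patients who restarted.

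The cost is reprogramming one table from dosing and event dates already collected. The intermittent group will have fewer patient-years and wider confidence intervals.

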10.2 Demographics and Registry Enrollment Characteristics

Demographics and baseline characteristics will be summarized for the All Treated Patient Population, the New Prescription Patient Population, and the Intermittent Treatment Population. Descriptive statistics will be presented. Number of patients with non-missing values, mean, and standard deviation will be provided for continuous variables. Counts and percentages will be provided for categorical variables. The number and percentage of patients that discontinue from the registry will be summarized, overall and by reason for discontinuation. Duration of observation in the registry and total duration of treatment will be summarized as follows:

Duration of observation in the registry is defined from the first day in the registry (enrollment visit or date of informed consent, up to the end-of-registry (as defined in Section 12.0).

The duration of treatment in the registry (registry exposure) is defined from the first dose of HUMIRA® in the registry to 14 days after the last dose of HUMIRA® excluding total days of any treatment interruptions.

Total duration of treatment (total exposure) is defined from the first recorded dose of HUMIRA® (initial dose) to 14 days after the last dose of HUMIRA® excluding total days of any treatment interruptions.

Time to observational and treatment discontinuation will also be presented as Kaplan-Meier (KM) curves.

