If treatment with HUMIRA® is permanently discontinued for any reason, patients will be encouraged to remain in the registry. If a patient discontinues the registry, the physician will offer the patient participation in the direct to HCP Process, as applicable per local regulations, regardless of HUMIRA® treatment. Patients that have affirmatively

withdrawn their authorization to have their personal health information used or disclosed in connection with the registry will not be asked to continue in the registry or asked to participate in the HCP Process.

For patients who discontinue the registry, physicians will be asked to obtain the patient's signature on a Patient Authorization for Use/Disclosure of Data form for the completion of a simplified Healthcare Provider (HCP) questionnaire on an annual basis, as applicable per local regulations. The first data collection period will capture data from the date of the patient's discontinuation visit or last contact in the registry through the completion of the first annual HCP questionnaire for the patient. The questionnaire focuses on the collection of surgeries, hospitalizations, deaths, and the events listed as AEs of Special Interest (Table 2), AEs of Special Interest that lead to permanent discontinuation of HUMIRA®, and psoriasis related medication use since registry discontinuation. The questionnaire may be completed by the registry physician or the patient's current HCP (if they are no longer under the care of a registry physician). Any other SAEs experienced should be reported according to standard spontaneous reporting procedures, and they are not subject to the requirements of this protocol.

Effectiveness measures will not be collected from patients participating in direct to HCP Process.

All patients that are unreachable after three consecutive documented attempts to contact the patient via phone, email, or certified letter, will be considered lost to follow-up.

AbbVie will take reasonable actions to ascertain vital status at the end of the patient's 10-year observational period. AbbVie will make every effort to work through investigational sites to match patients lost to follow-up against the National Death Index (NDI) in the US, national/regional cancer registries and vital registries as available in other countries and as allowed per local regulations.

The registry procedures to be conducted in the registry are outlined in the schematic presented in Table 1.

[figure not shown]

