10.3.1 Analysis of Observational AEs

The number and percent of patients experiencing SAEs, AEs of Special Interest and AEs that lead to permanent discontinuation of HUMIRA® during the registry, regardless of whether the AEs are reported during or after the HUMIRA® treatment, will be tabulated by body system and Medical Dictionary for Drug Regulatory Activities (MedDRA) preferred term. Rates (event per 100 patient-year of observation) of SAEs and AEs of Special Interest and the 95% confidence interval will be provided. The analysis will be performed using data from first day in the registry to the date of last contact for the All Treated Patient Population. The last contact date is defined as the last date of registry or direct to HCP process participation, whichever occurs later.

Standardized incidence ratios (SIRs) will be used to compare the rates of events in this registry to the general population.

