10.6 Determination of Sample Size

The proposed sample size for this registry of a minimum of 5,000 patients is based on the lowest frequency AE of Special Interest (i.e., lymphoma) seen in HUMIRA [®] clinical trials.

According to the latest US National Cancer Institute Surveillance Epidemiology and End Results (SEER) data, the age adjusted incidence rate of lymphoma in the general US population was 22.0 per 100,000 person-years during 2000-2004. Literature review has indicated a similar rate of 22.6/100,000 PY as reported by Gelfand and Margolis⁵ in a control psoriasis population using the General Practice Research Database (GPRD) in the UK. However, the lymphoma rate was 47.7/100,000 PY in the psoriasis patient population that excluded mild cases (defined as those who had not previously received systemic therapy). Other studies have previously reported a higher rate of 56.0/100,000 PY in an older psoriasis patient population with an average age of 59, excluding cutaneous T cell lymphoma. Therefore, the data reported by Gelfand and Margolis were considered the most appropriate basis for calculation of the sample size for this registry.

Using the rate of 0.0477/100 PY from this reference as representative of patients that would be eligible for biological therapy for the treatment of psoriasis, a total of 21500 PY of observation time is needed to provide 80% power to rule out the doubling of 0.0477/100 PY with a 1-sided 95% CI, i.e., the upper bound of the one-sided confidence interval is < 0.0954/100 PY.

[figure not shown]
Using an expected patient year attrition rate of 40%, the ten-year registry of 5,000 patients will provide an expected 30,000 PY of observation. When considering the additional 1,000 patients who will be permitted to enter the registry from outside US and Canada, the ten-year registry of 6,000 patients will provide an expected 36,000 PY of observation. This will markedly exceed the number of patient-years of observation necessary to rule out the doubling of the lymphoma rate among moderate-to-severe psoriasis patients.

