12.0 Completion of the Registry

The physician will conduct this registry in compliance with the protocol and all applicable regulatory and legal requirements. AbbVie may terminate this registry at any time, either in its entirety or at a site, for reasonable cause provided that written notice is submitted at a reasonable time in advance of the intended termination. The physician may also terminate the registry at their site for reasonable cause, after providing written notice to AbbVie a reasonable time in advance of the intended termination.

The end-of-registry is defined as the date of the last patient's visit in the registry or the HCP Process, whichever occurs later.

[figure not shown]

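### Section 10.2 ends observation time at one registry-wide date, but observational AEs are counted only to each patient's last contact; used as written, the definition biases observational rates low

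*Protocol*

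**What the plan says.** Four places in the protocol bear on this.

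- Section 10.2 defines duration of observation as running "from the first day in the registry (enrollment visit or date of informed consent, up to the end-of-registry (as defined in Section 12.0"). No other section defines observation time.
- Section 12.0 states: "The end-of-registry is defined as the date of the last patient's visit in the registry or the HCP Process, whichever occurs later". Read as written, this is one calendar date for everybody.
- Section 10.3 closes the observational AE window at last contact, and Section 10.3.1 defines that at patient level: "The last contact date is defined as the last date of registry or direct to HCP process participation, whichever occurs later". Section 10.3.1 reports these AEs as rates per 100 patient-years of observation and adds standardized incidence ratios (SIRs). Section 10.3.4 does the same for the analysis without the direct-to-HCP follow-up, again per patient-year of observation.
- Section 10.6 sizes the registry on lymphoma: "a total of 21500 PY of observation time is needed to provide 80% power to rule out the doubling of 0.0477/100 PY", with the criterion that "the upper bound of the one-sided confidence interval is < 0.0954/100 PY". It then projects the available time: "Using an expected patient year attrition rate of 40%, the ten-year registry of 5,000 patients will provide an expected 30,000 PY of observation".

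The Amendment 3 rationale in Section 1.1 says the durations were revised so that they would match the AE definitions.

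**The concern.** A rate needs its events and its person-time to stop on the same date. Here the events stop when the patient is last seen, while the time, as defined in 10.2, continues until the last patient in the registry has finished. A patient lost in year 1 would add about nine or more years during which none of that patient's events could be counted. A patient who completes Month 120 early in the calendar would keep adding time afterwards.

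The resulting bias has one direction: it makes the drug look safer. Long-term safety is the primary objective, the registry is a post-marketing commitment to FDA and EMA, and observational rates are among its five main safety analyses. The lymphoma question that sized the registry depends directly on this denominator.

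**Working it through.** **Inputs, all from Section 10.6 unless noted.** Reference rate r0 = 0.0477/100 PY ("Using the rate of 0.0477/100 PY from this reference as representative of patients that would be eligible for biological therapy"). Margin r1 = 2 × r0 = 0.0954/100 PY. One-sided 95% limit, 80% power. Attrition is 40% of patient-years. There are 5,000 or 6,000 patients. Follow-up is 10 years per patient (Section 6.4).

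**1. The protocol's own figures.** One-sample Poisson rate, normal approximation:

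PY = (1.645·√r1 + 0.842·√r0)² / (r1 − r0)², with r0 = 0.000477 and r1 = 0.000954 per PY, gives 21,038.

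This is 2.1% below the stated 21,500. With the exact Poisson limit, 21,500 PY allows 12 cases and gives 76.7% power; 80% is met at 21,670 PY (13 cases), although exact power moves in a sawtooth. The stated figure is reproduced closely enough and is not in dispute.

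Expected time also reproduces: 5,000 × 10 × 0.6 = 30,000 PY and 6,000 × 10 × 0.6 = 36,000 PY.

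**2. Denominator under 10.2.** Assume the registry runs until the last-enrolled patients reach Month 120. Every patient is then credited with at least 10 years: at least 6,000 × 10 = 60,000 PY (5,000 patients: 50,000). Observed over credited time is 36,000 / 60,000 = 0.60. At a true doubling the expected count is 0.000954 × 36,000 = 34.3 cases. The apparent rate is 34.3 / 60,000 = 0.0572/100 PY, only 1.2 times the reference.

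**3. Effect on the rule-out.** The exact upper limit for x cases is U(x) = ½·χ²(0.95; 2x + 2) / PY. The cut-off is the largest x with U(x) < 0.000954. Its probability is taken under a Poisson mean of r1 × observed PY.

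| Observed PY | Denominator PY | Cut-off (cases) | P(doubling ruled out, given a true doubling) |
|---|---|---|---|
| 36,000 | 36,000 | 24 | 4.1% |
| 36,000 | 60,000 | 44 | 95.4% |
| 30,000 | 30,000 | 19 | 3.8% |
| 30,000 | 50,000 | 36 | 92.5% |

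For example, 34 cases give an upper limit of 0.1257/100 PY on 36,000 PY, so doubling is not excluded. On 60,000 PY the limit is 0.0754/100 PY, and doubling appears to be excluded.

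**4. Sensitivity.** The losses below 40% and both accrual periods are assumptions; the documents do not give them. All rows have 36,000 observed PY.

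| Scenario | Denominator PY | Cut-off (cases) | P(doubling ruled out, given a true doubling) |
|---|---|---|---|
| 10% of time lost | 40,000 | 27 | 11.9% |
| 20% lost | 45,000 | 31 | 32.2% |
| 25% lost | 48,000 | 34 | 52.2% |
| 40% lost (protocol) | 60,000 | 44 | 95.4% |
| 40% lost, uniform accrual over 3 years | 6,000 × 11.5 = 69,000 | 52 | 99.8% |
| 40% lost, uniform accrual over 5 years | 6,000 × 12.5 = 75,000 | 57 | >99.9% |

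**The case against.** The strongest reply is that the protocol's authors did not mean a registry-wide denominator, and several passages support that.

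- Section 10.3.1 says its analysis uses data to the date of last contact, directly after naming the rates. It does not cite 10.2, whereas 10.3.2 does so for exposure. Section 10.2 presents its durations as quantities to be summarized.
- Section 10.6 speaks of PY of observation net of attrition. The figure of 60,000 PY appears nowhere in the protocol.
- Section 10.2 also plans Kaplan-Meier curves of time to observational discontinuation, which need patient-level end dates.
- Section 10.3 uses end-of-registry loosely: four analyses are said to run through it, but their event windows are then closed earlier.

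This stands as evidence of intent. A reader might infer from 10.2 and 12.0 that every observational rate will be too low and that a doubling of lymphoma would appear excluded. The documents do not support that as an unconditional statement: it follows only if the 10.2 definition is the denominator, and the rule-out figure also depends on the loss. Nor do they say whether the 40% is before or after HCP follow-up. The one-sided criterion appears only in the sample-size section; 10.3.1 asks for a 95% confidence interval and SIRs.

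The reply does not remove the contradiction. Section 10.3.1 gives no definition of observation time of its own, and the one definition available conflicts with it. The planned matching of lost patients to death and cancer registries (Section 6.5) does not help, because the event window still closes at last contact.

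A reader might also infer a further downward bias in SAE rates from HCP time, since Section 6.5 says of that period: "Any other SAEs experienced should be reported according to standard spontaneous reporting procedures, and they are not subject to the requirements of this protocol". That is a separate matter of unknown size. Section 7.4 has SAEs reported during the HCP process as well, and 10.3.4 already supplies an observational analysis without it. It is not part of this point.

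**Conclusion.** The contradiction is real and lies wholly in current text. The start of observation agrees with the AE window, but the end does not, despite the stated aim of aligning them. The bias is conditional. Used as written, with 40% of patient-years lost and the registry run to its full length, the 10.2 definition gives observational rates at most about 60% of their true value. The 10.6 criterion would then pass a true doubling of lymphoma about 95% of the time with 6,000 patients, or 93% with 5,000, instead of about 4%. The distortion is smaller with less loss and larger with staggered entry. SIRs would be affected in the same direction if their expected counts used the same time.

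The point concerns the observational analyses (10.3.1 and 10.3.4) only. Treatment-emergent rates use exposure time, and the 21,500 PY requirement is not affected. The definition should be corrected before it is programmed, because a later analysis plan that follows it faithfully would inherit the error.

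**What to change.** In Section 10.2, end duration of observation at the patient's last contact date as Section 10.3.1 defines it, in place of the end-of-registry in Section 12.0. For Section 10.3.4, end person-time at the last registry contact, leaving out HCP follow-up. State in 10.3.1 and 10.3.4 that this time is the denominator of the rates, and in 10.3.1 that it is also the person-time behind the SIRs. Section 12.0 can keep its definition for closing the registry.

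The cost is a few words and the matching programming; no new data are needed. If any interim report has already used the registry-wide date, its patient-years would fall and its rates would rise when recalculated.
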